## ABSTRACT

Hepatoblastoma is the most common malignant liver neoplasm in children. Although surgical resection is the mainstay of curative therapy for children with hepatoblastoma, only one-third to one-half of newly diagnosed patients with hepatoblastoma can be expected to have resectable disease at presentation. Patients who undergo a primary complete resection of their tumor have an excellent prognosis (90% event-free survival [EFS]). The use of chemotherapy has improved survival in patients with unresectable hepatoblastoma by increasing the number of patients whose tumors can be resected. However, more recent trials over the last decade have failed to significantly improve survival numbers. Therefore, the current EFS for the entire group of patients with non-metastatic, unresectable hepatoblastoma at diagnosis remains suboptimal (< 70%) and warrants novel treatment approaches. The survival of patients with metastatic disease at diagnosis remains poor (20-30%) and also requires consideration of novel therapeutic strategies. AHEP0731 builds on the results of the last 20 years of hepatoblastoma clinical trials and seeks to diminish toxicity in the approximately 30% of low-risk patients, increase survival in intermediate-risk patients and identify new agents(s) that may be used in high-risk and recurrent patients. Patients will be staged for risk classification and treatment at diagnosis using COG staging guidelines (see [Appendix III](#)). Study enrollment for patients with Stage I and II tumors is contingent on rapid central pathologic review of tumor specimens. All patients with Stage I pure fetal histology (PFH) hepatoblastoma will be classified as very low-risk and will be treated with surgery only. Patients with Stage I non-PFH, non-small cell undifferentiated (SCU) hepatoblastoma or with Stage II non-SCU hepatoblastoma will be classified as low-risk and will be treated on Regimen T with 2 adjuvant cycles of cisplatin, 5-fluorouracil, and vincristine (C5V), a reduction from the standard 4 cycles of chemotherapy used in previous COG trials. Patients with Stage I SCU, Stage II SCU, or any Stage III hepatoblastoma will be classified as intermediate-risk and will be treated with Regimen F (intermediate risk, stratum 3, has been closed to accrual as of 03/12/12). This treatment regimen is based on previous COG trials which administered 6 cycles of C5V therapy plus surgical resection of the tumor. However, to improve resection and survival rates, doxorubicin, an agent with proven efficacy will be added to the C5V therapy (C5VD). Surgical resection is necessary for cure and surgical resection whether by primary resection or orthotopic liver transplant (OLT) is intended after 4 cycles of intermediate-risk therapy. This trial will assess the feasibility in a cooperative group setting of timely referral (by the completion of Cycle 2) for OLT in children with hepatoblastoma designated as potentially unresectable following central surgical review and staging according to the PRETEXT (Pretreatment Extent of Disease) grouping system. AHEP0731 also aims to determine if PRETEXT grouping can predict tumor resectability and to assess if institutional assessment of PRETEXT grouping is reliable by comparing to PRETEXT grouping as performed by central review. All patients with any Stage IV hepatoblastoma as well as patients with any stage of hepatoblastoma and initial AFP <100 ng/mL will be classified as high-risk and will be treated with the novel combination of vincristine, irinotecan and temsirolimus in Regimen H in order to estimate the response rate of this new combination of agents. This regimen includes 2 cycles of “up-front” vincristine, irinotecan and temsirolimus in the initial 6 weeks of therapy. Patients who respond to vincristine/irinotecan/temsirolimus (VIT) will continue to receive this combination. Responding patients

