#### 1.2.4

To determine whether timely (between diagnosis and end of second cycle of chemotherapy) consultation with a treatment center with surgical expertise in major pediatric liver resection and transplant can be achieved in 70% of patients with potentially unresectable hepatoblastoma.

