Stage III: PRETEXT 2 multifocal = 1  
 PRETEXT 3 multifocal or +V or +P = 8  
 PRETEXT 4 = 13  
 Stage IV: PRETEXT 2 multifocal = 0  
 PRETEXT 3 multifocal or +V or +P = 2  
 PRETEXT 4 = 8  
 Total = 32

INT-0098 was open for enrollment for 4 years. As a conservative estimate, using the 32 patients as the projected number of patients for whom referral is appropriate, we expect referral will be appropriate for approximately 25 patients enrolled to AHEP0731.

Patients enrolled on this study will be considered candidates for referral provided the patient has a referable stage of disease and receives two cycles of chemotherapy and is still considered on protocol therapy at the end of the second cycle. A patient will be considered a referral success if: (1) the patient is enrolled on regimen F or regimen H and referred for transplant prior to the start of the third cycle of chemotherapy; or (2) the patient is enrolled on regimen H or W and is referred for transplant by the start of the third cycle of C5VD. Otherwise the patient will be considered a referral failure. In particular, a patient who has a referable stage of disease, is treated on regimen H or W and has protocol therapy terminated after the completion of cycle 2 but before the completion of cycle 4 without being referred for transplant will be considered a referral failure.

The feasibility of referral will be evaluated for each of the expected 25 patients who would be amenable to OLT. A patient for whom referral is considered appropriate who receives a consultation after enrollment will be considered a success with respect to feasibility. If referral is accomplished for 16 or more patients, the strategy will be considered successful and identified for possible incorporation into a randomized study. The characteristics of this rule as a function of the true 'success' probability are:

True Probability of Successful Referral	Chance Referral Will be Identified as Feasible
0.50	11%
0.55	24%
0.60	42%
0.65	63%
0.70	81%
0.75	93%

If more than 25 patients are identified as candidates for referral, the number of patients for whom referral

is accomplished required to consider referral “feasible” will be increased in such a way as to yield “Chance Referral Will be Identified as Feasible” probabilities of greater than 80% for the scenarios identified by the last two lines in the table above.

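### Section 9.2 defines referral success by a deadline, then places an untimed success sentence directly before the 16-of-25 cutoff for primary aim 1.2.4

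*Combined protocol and SAP*

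**What the plan says.** Primary aim 1.2.4 asks whether "timely (between diagnosis and end of second cycle of chemotherapy) consultation with a treatment center" with the relevant expertise can be achieved in 70% of potentially unresectable patients. The Abstract speaks of "timely referral (by the completion of Cycle 2) for OLT in children with hepatoblastoma".

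Section 9.2, Hypothesis 2.0, defines success in two clauses joined by 'or':

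- "1) the patient is enrolled on regimen F or regimen H and referred for transplant prior to the start of the third cycle" of chemotherapy;
- "2) the patient is enrolled on regimen H or W and is referred for transplant by the start of the third cycle of C5VD".

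It then closes the definition: "Otherwise the patient will be considered a referral failure".

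The next paragraph expects 25 candidates and states: "A patient for whom referral is considered appropriate who receives a consultation after enrollment will be considered a success with respect to feasibility". The decision rule follows at once: "If referral is accomplished for 16 or more patients, the strategy will be considered successful and identified for possible incorporation into a randomized study". A table gives the chance of a feasible verdict for true success probabilities from 0.50 to 0.75. A further paragraph, opening "If more than 25 patients are identified as candidates for referral", raises the cutoff so that this chance stays above 80% at 0.70 and 0.75.

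**The concern.** The two success statements classify some patients in opposite ways. A candidate first consulted after the deadline is a failure under the definition and a success under the sentence that leads into the cutoff. A candidate first consulted between diagnosis and enrollment is a success under the definition, which sets no earliest date, but does not literally meet the later sentence. The cutoff sentence says only that referral is accomplished and does not refer back to the definition.

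Timing is the substance of this aim. Section 2.6 says that a later randomized trial would probably fail unless suitable patients reach transplant centers in time. A count without a deadline would not answer that question, and a count starting at enrollment would discard some of the earliest referrals.

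There is a smaller problem inside the timed definition. Regimen H appears in both clauses, so its earlier limit has no effect. The limit that then governs, the start of the third C5VD cycle, is Cycle 5 on Regimen H (Section 7.5, footnote 4). Aim 1.2.4 refers to the end of the second cycle.

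**Working it through.** **1. Reproduce the plan's table.** Inputs from Section 9.2: n = 25, cutoff 16. The chance of a feasible verdict is P(X ≥ 16) with X ~ Binomial(25, p).

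| p | Plan | Recomputed |
|---|---|---|
| 0.50 | 11% | 0.115 |
| 0.55 | 24% | 0.242 |
| 0.60 | 42% | 0.425 |
| 0.65 | 63% | 0.630 |
| 0.70 | 81% | 0.811 |
| 0.75 | 93% | 0.929 |

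All six entries agree. The arithmetic is sound; the open question is what p measures.

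**2. Classify patients under each rule.**

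| First consultation | Timed definition | Untimed sentence, literally |
|---|---|---|
| Between diagnosis and enrollment | success | not counted |
| After enrollment, within the limit | success | success |
| After the limit | failure | success |
| Never | failure | failure |

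The rules disagree in the first and third rows, in opposite directions.

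**3. Effect on the decision rule.** Let t be the true timely rate, l the share of non-timely patients consulted late, and e the share of timely patients first consulted before enrollment. Under the timed definition p = t. Under the literal sentence p = t(1 − e) + (1 − t)l. The documents give neither l nor e, so the 10% values are assumptions.

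| t | l | e | p under the sentence | P(feasible), timed | P(feasible), sentence |
|---|---|---|---|---|---|
| 0.50 | 0.10 | 0 | 0.50 + 0.05 = 0.55 | 0.115 | 0.242 |
| 0.70 | 0.10 | 0 | 0.70 + 0.03 = 0.73 | 0.811 | 0.890 |
| 0.50 | 0.10 | 0.10 | 0.45 + 0.05 = 0.50 | 0.115 | 0.115 |
| 0.70 | 0.10 | 0.10 | 0.63 + 0.03 = 0.66 | 0.811 | 0.670 |

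A smaller late share of 5%, with e = 0, gives p = 0.525 and 0.171 at t = 0.50, and p = 0.715 and 0.853 at t = 0.70.

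The sign of the shift is the sign of (1 − t)l − te. It is upward only while late consultations outnumber pre-enrollment ones.

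**4. Is a pre-enrollment consultation plausible?** Yes. Sections 4.5 and 4.6 date a consultation from its first occurrence. Sections 4.6 and 13.1.3 encourage it at diagnosis. Section 3.1.5 allows up to 42 days from biopsy or surgery to the start of therapy, with enrollment before treatment.

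**The case against.** The strongest reply is that the disputed sentence is loose shorthand and the intended rule is clear. The timed text is a complete definition with a closing failure clause. The column heading of the operating-characteristics table refers to successful referral, which echoes that definition. Section 13.4 divides patients by whether they were successfully referred in time. The Abstract, aim 1.2.4 and Section 2.6 all require timeliness. This stands: a reader might infer that the plan leaves the choice of rule open, or adopts the untimed one, and the documents support neither inference. What remains is a literal contradiction at the point where the count is made, with no cross-reference to settle it.

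A second reply is that the error need not favor a feasible verdict. This also stands. A reader might infer that the sentence always inflates the result, but that holds only if no timely patient was first consulted before enrollment, or too few to offset the late ones. The last two rows of the table in step 3 show no change and a fall.

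A third reply is that the third-C5VD-cycle limit for Regimen H is deliberate. It recurs in Sections 4.6, 7.5, 13.1.3 and 13.1.5 and in the Regimen H delivery maps, and that regimen opens with two window cycles. On Regimen F every cycle is C5VD, so there the limit falls next to the end of cycle 2. The documents therefore do not show the limit to be a mistake. They do show Regimen H listed twice, and an aim whose wording does not say which cycles it counts.

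**Conclusion.** The contradiction is real and should be corrected, although the intended rule is not seriously in doubt. The sentence before the cutoff omits the deadline and, taken literally, also omits consultations before enrollment. It can misclassify patients in either direction.

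The plan's table is correct as arithmetic and answers aim 1.2.4 only when success means timely referral. With 10% late shares, the chance of a feasible verdict moves from 0.115 to 0.242 at 50% timely and from 0.811 to 0.890 at 70%. With 10% of timely patients also consulted before enrollment, it is unchanged at 50% and falls to 0.670 at 70%. These figures rest on assumed shares and on n = 25; they illustrate sensitivity and do not estimate bias.

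The consequence is limited, because the rule only flags referral for possible use in a later randomized study. The documents do not support concluding that the feasibility test is invalid or that its sample size or cutoff is wrong.

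**What to change.** - Delete the untimed sentence, or replace it with a reference to the timed definition.
- State that the cutoff (16 of 25, or the raised value if there are more than 25 candidates) counts only timed successes. Consultations between diagnosis and enrollment are included, and late ones are failures.
- Have the sponsor reconcile the two clauses that both name Regimen H, and the third-C5VD-cycle limit with the wording of aim 1.2.4. This review does not choose the deadline.
- The document records closure on July 20, 2018, so record, with a date, whether the clarification was made without knowledge of the referral counts.

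The cost is one sentence and one clause in Section 9.2 and a clarification of aim 1.2.4. Sample size, cutoff and table stay as they are. Consultation dates must be checked against the limits, and the reported referral rate may change slightly.

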All patients who are referred for OLT evaluation and considered candidates for such a surgery will contribute to the evaluation of secondary aim 1.3.2. If we conclude referral is feasible, we estimated conservatively 16 patients would be referred. We estimate that 2 such patients will not be candidates for OLT because of technical reasons. If 8 or more of the 14 patients considered candidates for OLT receive such a procedure, OLT will be considered a candidate for possible incorporation into a randomized trial. The characteristics of this rule as a function of the true ‘success’ probability is:

Probability of OLT Performed on a Potential Candidate	Chance OLT will be Identified for Possible Incorporation Into a Randomized Trial
0.50	0.40
0.55	0.55
0.60	0.69
0.65	0.82
0.70	0.90
0.75	0.96

If more than 14 patients are successfully referred for OLT the current cutoff of 8 noted in the paragraph above will be increased in a manner similar to that described for the analysis of feasibility of referral.

Any patient from this secondary endpoint analysis population that receives an OLT will be considered a success with respect to the secondary aim 1.3.3. All patients in this cohort will be further subdivided into one of four outcome-of-transplant attempt groups: (a) proven to be resectable with a conventional surgery; (b) remain unresectable, primary transplant performed after a good initial response to chemotherapy; (c) remain unresectable, no surgery performed due to persistent metastatic disease unresponsive to chemotherapy or surgical resection; or (d) do not proceed to surgery because of refusal or deteriorating patient condition.

Two years after the last patient is enrolled we will calculate the 95% confidence interval for the 2-year EFS. If OLT is considered for possible incorporation into a randomized trial, we estimate conservatively that 8 patients will have undergone an OLT. The expected width of the 95% confidence interval is:

Expected 95% Confidence Interval Widths as a Function of the True 2-Year EFS

True 2-Year EFS	Expected 95% Confidence Interval for 2-Year EFS
0.50	0.17-0.83
0.60	0.24-0.88
0.70	0.32-0.93
0.80	0.42-0.97
0.90	0.54-0.99

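### The clause that raises the OLT cut-off for aim 1.3.2 counts referred patients, while the 8-of-14 rule counts OLT candidates, so it calls for an increase its own criterion rules out

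*Combined protocol and SAP*

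**What the plan says.** All of this is in Section 9.2 of the combined protocol and SAP, under Hypothesis 2.0 (Referral Feasibility).

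- **Referral rule (aim 1.2.4).** The expected number is given as "we expect referral will be appropriate for approximately 25 patients enrolled to AHEP0731", and "If referral is accomplished for 16 or more patients, the strategy will be considered successful". If there turn out to be more than 25 candidates for referral, the cut-off is raised so as to keep "probabilities of greater than 80% for the scenarios identified by the last two lines in the table above". Those lines are true probabilities of 0.70 and 0.75.
- **OLT population (aim 1.3.2).** "All patients who are referred for OLT evaluation and considered candidates for such a surgery will contribute to the evaluation of secondary aim 1.3.2".
- **OLT planning numbers.** "If we conclude referral is feasible, we estimated conservatively 16 patients would be referred". Then: "We estimate that 2 such patients will not be candidates for OLT because of technical reasons". That leaves 14.
- **OLT rule.** "If 8 or more of the 14 patients considered candidates for OLT receive such a procedure", OLT is put forward for possible use in a randomized trial. The table beneath is labelled by the probability that a potential candidate is transplanted.
- **OLT adjustment clause.** "If more than 14 patients are successfully referred for OLT the current cutoff of 8 noted in the paragraph above will be increased". The approach is to be modelled on the referral adjustment.

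**The concern.** The population, the rule and the table for aim 1.3.2 all count candidates. The trigger counts successful referrals, which the same section defines separately by timing and which the plan itself puts at 16 when there are 14 candidates. The referral clause that serves as the model does not have this mismatch: its trigger uses the denominator of its own rule.

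The clause is therefore active in the very scenario from which the 14 was derived, and it tells the analyst to raise a cut-off that the cited method does not allow to rise. At stake is a pre-specified go/no-go rule that would have to be interpreted after the counts are known. Someone reading the trigger literally could also size a new cut-off on the referred patients and arrive at a materially stricter rule than the printed one.

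**Working it through.** **Inputs (Section 9.2).** Referral: n = 25, cut-off 16. OLT: 16 referred, 2 non-candidates, n = 14, cut-off 8. Trigger: more than 14 successfully referred. Criterion: chance above 80% at p = 0.70 and at p = 0.75.

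**Formula.** P(X ≥ r) = Σ C(n,k) pᵏ(1−p)ⁿ⁻ᵏ, summed over k = r to n.

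**Step 1: reproduce the printed tables.**

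| True p | 0.50 | 0.55 | 0.60 | 0.65 | 0.70 | 0.75 |
|---|---|---|---|---|---|---|
| Referral, printed | 11% | 24% | 42% | 63% | 81% | 93% |
| ≥16 of 25, exact | 0.115 | 0.242 | 0.425 | 0.630 | 0.811 | 0.929 |
| OLT, printed | 0.40 | 0.55 | 0.69 | 0.82 | 0.90 | 0.96 |
| ≥8 of 14, exact | 0.395 | 0.546 | 0.692 | 0.816 | 0.907 | 0.962 |

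Both agree to within a percentage point. The OLT table is therefore a table for 14 candidates.

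**Step 2: when does the clause fire?** In the base case, 16 referred > 14, so it fires although candidates number 16 − 2 = 14. Feasible referral needs at least 16, and the plan's own adjustment can only raise that number, so every feasible result fires it. It stays off only at 14 or fewer referrals, which is a failed referral result.

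**Step 3: what increase does the cited method permit?** The highest cut-off with more than 80% at both 0.70 and 0.75 is:

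| Candidates | Highest cut-off | At 0.70 | At 0.75 |
|---|---|---|---|
| 12 | 7 | 0.882 | 0.946 |
| 13 | 8 | 0.835 | 0.920 |
| 14 | 8 | 0.907 | 0.962 |
| 15 | 9 | 0.869 | 0.943 |
| 16 | 10 | 0.825 | 0.920 |

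With 14 candidates, 9 gives 0.781 at 0.70 and 0.888 at 0.75, so it fails at 0.70. With 14 or fewer candidates, no cut-off above 8 qualifies.

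**Step 4: sizing on the referred group.** Using the 16 referred as n gives a cut-off of 10. The two non-candidates are not expected to be transplanted, so in effect this asks for 10 of 14. The chance of meeting that at p = 0.70 is 0.584, against 0.907 for the printed rule.

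**Step 5: where the two triggers differ.** They differ only with 15 or more referred and 14 or fewer candidates. With more than 14 candidates, more than 14 have necessarily been referred, so both fire and the cited method works (for example 9 of 15).

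**The case against.** **The meaning is recoverable.** In this part of the section 14 appears only as the number of candidates, the model clause uses its own rule's denominator, and aim 1.3.2 itself speaks of OLT after successful referral. A statistician reading the whole section would probably take the trigger to mean more than 14 candidates. That is fair, and the fix adopts that reading. But the section defines referral success separately and distinguishes 16 referred from 14 candidates a few sentences before the clause, so the written text does not say it.

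**The cut-off need not move.** A reader might infer that 8 of 14 can never apply once referral succeeds, or that the cut-off becomes 9 with a loss of 21, 18 and 13 points at true rates of 0.60, 0.65 and 0.70 (0.692 − 0.486, 0.816 − 0.641, 0.907 − 0.781). The documents support neither. The clause never names 9, and its cited criterion excludes it with 14 candidates. An analyst who puts the criterion first stays at 8. Even if 9 were used, the decision would change only with exactly 14 candidates and exactly 8 transplants.

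**The disputed case may not arise.** Section 2.3.3 gives 83 Stage III and 40 Stage IV patients on INT-0098. Section 9.2 counts 32 of that trial's patients as referable: 32/123 = 26%. Enrolment here is 105 in stratum 3, about 30 on the initial window regimen (Section 2.3.4) and up to 43 on Regimen H, or 178. Then 178 × 0.26 ≈ 46 referable. Assuming referral rates of 0.50 to 0.75 and candidacy of 14/16, that gives roughly 20 to 30 candidates, where both triggers fire. This is rough: stratum 3 includes some Stage I and II patients, and PRETEXT group could be assigned for only 155 of the 182 INT-0098 patients. It does lower the practical importance. On the plan's own expectation of 25, however, 70% referral gives 17.5 referred and 17.5 × 14/16 = 15.3 candidates, close to the boundary.

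**Conclusion.** The defect is real but small. The trigger counts the wrong group, and in the base case the clause demands an increase that its own method forbids. The result is a contradiction, not a definite move to a stricter cut-off. It is confined to 15 or more referred with 14 or fewer candidates. The largest identifiable consequence comes from sizing the cut-off on the 16 referred: the chance of identifying OLT at a true rate of 0.70 would fall from 91% to 58% with 14 candidates.

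This rests on exact binomial calculation with independent patients, on the plan's 16 and 14, and on reading the manner of increase as the above-80% criterion at 0.70 and 0.75. The printed operating characteristics are correct. No primary endpoint or stopping rule depends on the clause; it bears only on whether OLT is put forward for a possible randomized trial.

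**What to change.** In Section 9.2, change the condition of the clause to: *If more than 14 referred patients are considered candidates for OLT*. Trigger, denominator and table then count the same patients. With 16 referred and 14 candidates the clause stays off, and 8 of 14 stands with its printed characteristics. Above 14 candidates the cited method gives workable cut-offs, such as 9 of 15 (0.869 at 0.70), 10 of 16 (0.825), 10 of 17 (0.895) and 11 of 18 (0.859).

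The cost is one phrase; no data, patients or recalculation of the table are needed. If the analysis has already been done, the report should state the numbers referred, the number of candidates and the cut-off applied.

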#### 1.3.3

To estimate the 2-year EFS for patients once identified as candidates for possible OLT, the 2-year EFS for patients referred to a transplant center that are resected without OLT, and the 2-year EFS for patients referred to a transplant center who receive OLT.

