#### 4.5 Treatment for Intermediate-Risk Patients (Stratum 3 - Regimen F)

**Note: Stratum 3 has been closed to accrual as of 03/12/12.**

All patients with Stage I SCU, Stage II SCU, and Stage III disease will be treated with Regimen F (C5VD). Patients will receive 4 cycles of therapy repeated every 21 days, followed by surgical resection of the tumor or liver transplant (OLT). Patients whose tumors are removed surgically or by OLT after Cycle 4 will receive 2 post-operative cycles of chemotherapy. Patients may have their tumor removed if deemed feasible after 2 cycles of chemotherapy but will then receive 4 cycles of post-operative chemotherapy. **All intermediate-risk patients will receive a total of 6 cycles of chemotherapy.** Patients whose tumors remain unresectable after 4 cycles will be considered off protocol therapy, but will continue to be followed on the AHEP0731 off protocol therapy follow-up CRF. These patients can at the discretion of the primary physician. Additional pre-operative cycles of chemotherapy after Cycle 4 are **NOT** permitted in an attempt to make the tumor resectable or if a liver is not available for transplantation. Patients with progressive disease at any time are off-protocol therapy.

Tumors that are unresectable at diagnosis should be referred to a surgical center with expertise in pediatric liver transplant and “extreme” liver resection as soon as possible. Optimally for planning purposes, this liver transplant consultation should be obtained but at the latest it should be done following the first 2 cycles of neoadjuvant chemotherapy. The consent for the PLUTO registry should be obtained within one month of undergoing liver transplant and is usually obtained by the liver transplant team.

For the purposes of this study, consultation will be defined and may be accomplished in one of two ways:

- The FIRST TIME the patient is seen face to face by the transplant physician/team in the same institution or another institution.
- The FIRST TIME radiographic films and referral material are sent to the transplant physician/team at the same or another institution and are formally reviewed by the transplant physician/team.

The transplant physician/team will communicate the result of this consultation back to the referring physician.

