Resection planning is to be completed before completion of the 4th cycle of chemotherapy. Transplant or “extreme” resection is intended to occur within 4 weeks of the completion of the 4th cycle of chemotherapy.

Chemotherapy should resume as soon as possible after surgical resection. In most circumstances this can typically be achieved within 3 weeks following surgery. Patients who do not resume post resection chemotherapy within 42 days of resection will be considered off protocol therapy. Further treatment will be at the discretion of the treating physician.

Patients classified as intermediate-risk will receive 6 cycles of C5VD. Surgical resection of tumor or liver transplant will occur following Cycle 2 (if feasible) or Cycle 4. All patients < 10 kg will have dosing in mg/kg.

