### 9.2 Statistical Analysis Methods

#### Statistical Considerations

Patients will be enrolled to the study for Five years and followed for an additional year, by which time we expect most disease-related analytic events will have occurred. The design objectives will be different for the four subgroups: (1) Stage I PFH patients (stratum 1) with AFP  $\geq$  100 ng/mL or AFP not obtained prior to surgical resection of tumor; (2) low risk patients (stratum 2) defined as patients with Stage I non-PFH, non-SCU; Stage II non-SCU (3) intermediate risk patients (stratum 3); and (4) Stage IV patients or patients with AFP < 100 ng/mL at diagnosis (stratum 4). EFS will be the time from patient enrollment until last follow-up or an analytic event is observed, whichever comes first. Analytic events are: (1) progression of existing disease or occurrence of disease at new sites; (2) treatment failure defined as the presence of disease after four cycles of chemotherapy and post-induction surgery (if attempted) for patients enrolled with Stage III disease or presence of disease after planned chemotherapy (eight cycles for non-responders, ten cycles for responders) for patients enrolled with Stage IV disease (3) death from any cause prior to disease progression or diagnosis of a second malignant neoplasm; or (4) diagnosis of a second malignant neoplasm. Survival will be the time from enrollment until death from any cause or last follow-up, whichever comes first.

[Section 3](#) requires that planned start of systemic therapy for patients whose protocol prescribed therapy includes chemotherapy must be within 42 days of enrollment. Experience from prior COG studies of hepatoblastoma demonstrates that this can be accomplished in most patients. All patients who die within 42 days of enrollment will be considered in the analytic plans below. All patients who survive more than 42 days after enrollment and whose protocol therapy prescribes chemotherapy but who do not have such systemic therapy started by the 43rd day after enrollment will be excluded from the analyses below.

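### Aim 1.3.3 times 2-year EFS from enrollment in groups defined by later surgery, which modestly inflates the estimates for transplanted and resected patients

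*Combined protocol and SAP*

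**What the plan says.** Section 9.2 has a single EFS definition: "EFS will be the time from patient enrollment until last follow-up or an analytic event is observed, whichever comes first". It makes no exception for any analysis.

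Aim 1.3.3 asks for 2-year EFS in three groups. The first is patients once they are identified as possible OLT candidates. The second is referred patients whose tumor is removed by an operation other than transplant. The third is worded as "the 2-year EFS for patients referred to a transplant center who receive OLT". The second and third groups are defined by an operation received after enrollment and referral.

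The referral-feasibility part of Section 9.2 fixes the time of analysis: "Two years after the last patient is enrolled we will calculate the 95% confidence interval for the 2-year EFS". That cut fits an enrollment origin. For precision, the plan says "we estimate conservatively that 8 patients will have undergone an OLT" and tabulates the expected 95% interval for true 2-year EFS from 0.50 to 0.90. It mentions no landmark, surgery-date origin, left truncation or time-dependent surgical status.

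**The concern.** To be counted as transplanted or resected, a patient must first live long enough to be operated on. The weeks before surgery still count toward the two years, although a death in those weeks would have kept the patient out of the group.

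Progression works in nearly the same way. It takes a patient off protocol therapy (Sections 4.5 and 8.1). Stage IV patients are offered OLT only after extrahepatic disease has cleared or been removed (Section 2.5). Early failures therefore fall mostly on the candidate group as a whole and hardly at all on the two surgical groups.

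The three estimates will probably be printed side by side. A reader who takes them at face value, or uses the OLT figure as an assumption in later planning, will be working with a value that is too high. The width of the interval does not show this, because the tabulated intervals describe sampling error only.

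**Working it through.** **1. The plan's own table.** With n = 8, I averaged exact (Clopper-Pearson) limits over a Binomial(8, p) distribution, using a one-sided 5% limit at 0 and 8 successes. The results, with the plan's figures in brackets:

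- p = 0.50: 0.174–0.826 (0.17–0.83)
- p = 0.60: 0.244–0.884 (0.24–0.88)
- p = 0.70: 0.325–0.931 (0.32–0.93)
- p = 0.80: 0.421–0.967 (0.42–0.97)
- p = 0.90: 0.538–0.990 (0.54–0.99)

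The table reproduces to rounding. It treats 2-year EFS as a simple proportion and makes no allowance for time before surgery. Interval widths run from 0.99 − 0.54 = 0.45 to 0.83 − 0.17 = 0.66.

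**2. Time from start of therapy to surgery.** Cycles last 21 days.

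- Regimen F (Section 4.5), resection after cycle 2: 2 × 3 = 6 weeks.
- Regimen F, after cycle 4: 4 × 3 = 12 weeks. Transplant or extreme resection "is intended to occur within 4 weeks of the completion of the" fourth cycle, so up to 12 + 4 = 16 weeks.
- Regimen H (Section 13.1.5), non-responders after cycle 6: 18 to 18 + 4 = 22 weeks.
- Regimen H, responders after cycle 7: 21 to 21 + 4 = 25 weeks.

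Section 4.6 instead names the end of cycle 6 as the latest intended point for responders too. The two sections need reconciling; week 25 serves here only as an upper bound. The range is therefore 6 to 25 weeks, or 6/104 = 6% to 25/104 = 24% of the two-year window. Enrollment precedes therapy, so the guaranteed time from enrollment is slightly longer.

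**3. Size of the shift.** Assume a constant hazard and that every group member is event-free at surgery in week t. Let S be the true 2-year EFS counted from surgery. The same patients counted from enrollment have EFS at week 104 of S^((104 − t)/104). For example, with S = 0.70 and t = 16, 0.70^(88/104) = 0.739, a shift of +3.9 points.

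| True S | t = 6 | t = 12 | t = 16 | t = 25 |
|---|---|---|---|---|
| 0.50 | 0.520 (+2.0) | 0.542 (+4.2) | 0.556 (+5.6) | 0.591 (+9.1) |
| 0.60 | 0.618 (+1.8) | 0.636 (+3.6) | 0.649 (+4.9) | 0.678 (+7.8) |
| 0.70 | 0.715 (+1.5) | 0.729 (+2.9) | 0.739 (+3.9) | 0.763 (+6.3) |
| 0.80 | 0.810 (+1.0) | 0.821 (+2.1) | 0.828 (+2.8) | 0.844 (+4.4) |
| 0.90 | 0.905 (+0.5) | 0.911 (+1.1) | 0.915 (+1.5) | 0.923 (+2.3) |

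**4. Other hazard shapes.** These were run for 2-year EFS of 0.50, 0.70 and 0.80 and surgery at weeks 16 and 25. If no events occur before surgery, the shift is +3.2 to +9.8 points. If the hazard is doubled before surgery and halved after year 2, it is +1.5 to +5.6. The sign is upward in every case run.

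**5. The candidate group.** Section 9.2 counts a patient as a referral candidate only after two cycles, while still on protocol therapy. That is 2 × 3 = 6 guaranteed weeks, so the t = 6 column (+0.5 to +2.0) applies to this group if it is timed from enrollment.

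**The case against.** The strongest reply is that nothing in the plan turns on these estimates. OLT is put forward for a randomized trial if at least 8 of 14 candidates receive it, and referral is judged by 16 of 25; neither rule uses EFS. Aim 1.3.3 only estimates, and no contrast between groups is specified. With 8 patients, one event is worth 1/8 = 12.5 points, more than any shift above. All of this stands, and it keeps the point small.

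A reader might infer that the plan would make surgery look superior, or would distort the decision about a randomized trial. The documents do not support that: the comparison is not planned and the decision rests on counts. Use of the EFS figures in later planning is plausible, but it is not a stated purpose.

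A reader might also infer that no event before surgery can occur in the surgical groups. That is strictly true only of death. Membership depends on receiving the operation, with no requirement to be event-free at that time. A patient who progressed could be operated on off protocol and, since follow-up continues, still be counted. The calculation's assumption that everyone is event-free at surgery therefore tends to overstate the shift somewhat.

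Finally, moving the origin to surgery removes the guaranteed time but not the selection of patients who reach surgery. That is also correct, and the fix has to say so.

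**Conclusion.** The concern holds as a modest bias in a descriptive secondary aim. As written, the plan counts time before surgery toward the 2-year EFS of the transplanted and resected groups, and the estimates are biased upward. Across the schedule the shift is about +0.5 to +9.1 points under a constant hazard, smallest for early resection with high EFS and largest for late surgery with low EFS. It is well inside the planned interval width, but it is systematic and nothing in the plan discloses it.

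The size rests on three assumptions: surgery at the protocol's intended times, all members event-free at surgery, and the hazard shapes tried. The documents give no event rate before surgery, so the range cannot be narrowed from them. The direction does not depend on the hazard shape in any case run.

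**What to change.** Amend Section 9.2 for aim 1.3.3 as follows.

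- For the OLT group and the group resected without OLT, measure 2-year EFS from the date of surgery.
- For the candidate group, measure it from the date the patient is identified as a candidate, which fits the wording of the aim. If two completed cycles remain an entry condition, that date should be no earlier than the day the condition is met.
- Alternatively, use one common landmark for all three groups at the planned surgical time point, chosen in advance, and include only patients event-free then.
- State that the three estimates are not to be compared causally, because selection into surgery remains under either option.

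The cost is small: analysis wording only, with no change to treatment, enrollment or sample size. Surgery dates are already needed for the 42-day rule on resuming chemotherapy, and operative reports are submitted (Section 14.1.2). With a surgery origin, the last patients would be up to about 25 weeks short of two years at the present cut. Either the read-out for the surgical groups moves by up to about 6 months, or those patients are censored before two years.
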